7.18. Pharmacodynamic Analyses

The pharmacodynamic (PD) endpoints of SHBG, lipid panel, FGF19, 7α C4, and bile acids are collected at the timepoints shown in Table 8 of the protocol.

The change from baseline in SHBG, LDL-c, will be analyzed in the same manner as specified in Section 7.7 and pairwise comparisons in Section 7.6 using the efficacy analysis set.

Plasma concentrations for $7\alpha C4$, FGF19, and bile acids that are BLQ will be set to $\frac{1}{2} \times BLQ$. Plasma PD parameters will be computed for PD patients only. Plasma PD parameters for $7\alpha C4$ and FGF19 will be calculated from the individual plasma concentrations using a non-compartmental approach for Day 1 and Week 12. Day 1 will include pre dose and all post dose assessments prior to dosing on Day 2. Week 12 will include pre dose and all post dose assessments. The actual PD sampling times will be used for the PD analysis. If actual PD sampling times are missing, nominal times will be used. Table 1 below presents the plasma PD parameters to be calculated.

Final, Version 2.0, 26JULY2023

CONFIDENTIAL

Labcorp Drug Development Study: 000000231152 Protocol Reference: TERNCB-2002

Table 10 Plasma PD Parameters

Abbreviation	Parameter Definition
AUEC ₀₋₂₄	Area under the effect-time curve from time 0 to 24 hours postdose
RAUEC	Ratio of AUEC (Week 12) /AUEC (Day 1).
C_{\min}	For $7\alpha C4$ only, minimum observed plasma concentration, obtained directly from the plasma concentration-time profiles. In the case where multiple minimums are of equal magnitude, the earliest minimum concentration will be reported as C_{min} .
RC _{min}	For $7\alpha C4$ only, ratio of $C_{min (Week 12)}/C_{min (Day 1)}$.
C _{max}	For FGF19 only, maximum observed plasma concentration, obtained directly from the plasma concentration-time profiles. In the case where multiple peaks are of equal magnitude, the earliest peak concentration will be reported as C_{max} .
RC _{max}	For FGF19 only, the ratio of $C_{max (Week 12)} / C_{max (Day 1)}$.
t _{min}	For $7\alpha C4$ only, time of the minimum observed plasma concentration, obtained directly from the plasma concentration-time profiles. In the case where multiple minimums are of equal magnitude, the time of the earliest minimum will be reported as the t_{min} .
t _{max}	For FGF19 only, time of the maximum observed plasma concentration, obtained directly from the plasma concentration-time profiles. In the case where multiple peaks are of equal magnitude, the time of the earliest peak will be reported as the t_{max} .

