9.4.4.3. Pharmacodynamic Endpoints

PD markers of THR- β agonism include SHBG and lipids, while PD markers of FXR agonism include FGF19, 7 α C4, and bile acids. Descriptive statistics of PD marker results, change from baseline, and percent change from baseline will be summarized by treatment group and visit. Change (and separately percent change) from baseline will be analyzed at applicable time points using the same ANCOVA model specified for the primary endpoint.

Pharmacodynamic parameters may also be calculated, summarized, and described by plotting the concentration-time curve or time-effect curve.

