Appendix 2: Sample Collection for Pharmacokinetics and Pharmacodynamics

Table 8 presents a description of PK/PD sample requirements at each study visit and timepoint.

Week	Day	Timepoint	Sample Type
0	1	Pre-dose (All Patients)	 Patients in PK/PD sub-study TERN-501, TERN-101, and TERN-101 metabolite TRN-000971 PK samples (PK/PD sub-study) Lipid Panel, 7αC4, FGF19, bile acids, and SHBG PD samples (PK/PD sub- study) Patients not participating in PK/PD sub- study Lipid Panel, 7αC4, bile acids, and SHBG PD samples
		 Post dose at the following timepoints (PK/PD sub-study only): 1 hour ± 5 minutes 2 hour ± 15 minutes 4 hours ± 15 minutes 6 hours ± 15 minutes 24 hours ± 1 hour prior to dosing on Day 2 	 TERN-501, TERN-101, and TERN-101 metabolite TRN-000971 PK samples 7αC4 and FGF19 PD samples
2	15 ± 3	Pre-dose (All Patients)	 TERN-501, TERN-101, and TERN-101 metabolite TRN-000971 PK samples Lipid Panel, 7αC4, and SHBG PD samples
4	29 ± 3	 Pre-dose (All Patients – PD samples) One sample between 2 and 6 hours post dose (All Patients – PK samples) 	 Lipid Panel, 7αC4, and SHBG PD samples TERN-501, TERN-101, and TERN-101 metabolite TRN-000971 PK samples
6	43 ± 3	Pre-dose (All Patients)	 TERN-501, TERN-101, and TERN-101 metabolite TRN-000971 PK samples Lipid Panel, 7αC4, and SHBG PD samples
8	57 ± 3	Pre-dose (All Patients)	TERN-501, TERN-101, and TERN-101 metabolite TRN-000971 PK samples
12	85±3	Pre-dose (All Patients)	 Patients in PK/PD sub-study TERN-501, TERN-101, and TERN-101 metabolite TRN-000971 PK samples Lipid Panel, 7αC4, FGF19, bile acids, and SHBG PD samples

Table 8PK/PD Sampling Timepoints

			 Patients not participating in PK/PD substudy TERN-501, TERN-101, and TERN-101 metabolite TRN-000971 PK samples Lipid Panel, 7αC4, bile acids, and SHBG PD samples
		 Post dose at the following timepoints (PK/PD sub-study only): 1 hour ± 5 minutes 2 hour ± 15 minutes 4 hours ± 15 minutes 6 hours ± 15 minutes 24 hours ± 1 hour on Day 86 PK only: 48 hours ± 2 hours on Day 87 72 hours ± 4 hours on Day 88 	 TERN-501, TERN-101, and TERN-101 metabolite TRN-000971 PK samples 7αC4 and FGF19 PD samples (up to 24 hours ± 1 hour on Day 86 only)
ET	ET	• At the ET Visit, for all patients discontinuing the study at any time for any reason (Early Termination)	 TERN-501, TERN-101, and TERN-101 metabolite TRN-000971 PK samples Lipid Panel, 7αC4, FGF19, bile acids, and SHBG PD samples

PD Sample Collection

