2.2.3.1. Endpoints for the Exploratory Objectives

- Change from baseline in the following parameters, as applicable:
 - o ALT, AST, and GGT
 - o FIB-4, CK-18 (M30 and M65), ELF (PIIINP, TIMP-1, HA), PRO-C3, and FAST score
 - TE and CAP
 - o MRI-PDFF (relative change) and cT1
 - o SHBG
 - o Lipid panel (for PD as well as safety evaluation)
 - o rT3
 - o FGF19, bile acids, and 7α C4
- Proportion of responders on MRI-PDFF and/or cT1 with the following:
 - \circ ≥ 30% relative reduction in MRI-PDFF
 - \circ ≥ 80 msec reduction in cT1
- PK parameters (e.g., AUC, C_{max}, C_{tau})

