7.7. Analysis and Reporting of Change and Relative Change from Baseline

Analysis of change and relative change will be performed using a type III sum of squares ANCOVA model with treatment group as a fixed effect and baseline covariate, where applicable. Least squares (LS) means and standard errors (SE) as well as 95% confidence intervals (CIs) will be presented for each treatment group at each scheduled visit.

LS estimates of the mean difference, SE, and 95% CI between each TERN active treatment group versus placebo comparison will be presented at scheduled visits. Analyses will include the pairwise comparisons in table 6 of Section 7.6 at week 12, unless otherwise specified. Relative change will include LS means, SE, and 95% CI but only MRI-PDFF relative change will include inferential statistics.

Table displays:

- (1) Observed result descriptive statistics, as described in Section 3.1, will be displayed within the same table.
- (2) All scheduled visits should be reported.
- (3) Pooling of treatment group should not be performed or displayed unless noted otherwise.

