8.5. Electrocardiograms

Summary statistics will be provided for heart rate, PR interval, QRS interval, QT interval, and QTcF at each visit. The investigator interpretation is collected as normal, abnormal not clinically significant (NCS), or abnormal clinically significant (CS). Patients whose interpretation shifts from normal to abnormal (CS or NCS) will be listed separately including description of the abnormality and any associated comments.

Categorical summaries will for baseline, worst post-baseline, and change from baseline for the following QTcF values will be presented:

- > 450 msec
- > 480 msec
- > 500 msec
- Change from baseline > 30 msec
- Change from baseline > 60 msec

CONFIDENTIAL

All ECG results will be presented in by-patient data listings. If applicable, cardiologist consult information will be presented in a separate by-patient data listing.

CONFIDENTIAL

9. Other Assessments

Other assessments will be provided in by-patient data listings only; no summary tables will be provided, including but not limited to the following:

- Eligibility details including unmet eligibility criteria
- Informed consent
- Randomization schema
- Physical examination collection information
- Serology
- Pregnancy testing
- FSH test
- Urine drug screen
- Alcohol test
- Urinalysis and Urine Microscopic Examination
- Coagulation
- Hemoglobin A1c
- Direct bilirubin
- Indirect bilirubin
- Laboratory reference ranges
- Cardiology consult
- Overdose
- Comments

Final, Version 2.0, 26JULY2023

CONFIDENTIAL

10. Changes to Protocol Planned Analyses

There were no changes from the protocol planned analyses.

CONFIDENTIAL

Statistical Analysis Plan CONFIDENTIAL Labcorp Drug Development Study: 000000231152 Protocol Reference: TERNCB-2002

11. Appendices

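### SAP 7.18 gives the protocol's planned ANCOVA only to SHBG and LDL-c; trough 7αC4, bile acids and eight of nine PD lipids have no between-group model, yet Section 10 declares no change

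*SAP*

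**What the plan says.** Protocol 9.4.4.3 names SHBG and lipids as markers of THR-β agonism, and FGF19, 7αC4 and bile acids as markers of FXR agonism. For all of them it plans: "Change (and separately percent change) from baseline will be analyzed at applicable time points using the same ANCOVA model specified for the primary endpoint". That model (protocol 9.4.2) has treatment group as a fixed effect and baseline as a covariate.

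The samples exist in every patient. For patients outside the PK/PD sub-study, protocol Table 8 (Appendix 2) lists at Day 1 and Week 12: "Lipid Panel, 7αC4, bile acids, and SHBG PD samples". Trough 7αC4 is also drawn in all patients at Weeks 2, 4 and 6. Pre-dose FGF19 at Day 1 and Week 12 is a sub-study sample only.

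The SAP repeats the endpoints. Section 2.2.3.1, under "Change from baseline in the following parameters, as applicable", still lists SHBG, the lipid panel, FGF19, bile acids and 7αC4. Section 7.18, however, states only "The change from baseline in SHBG, LDL-c, will be analyzed in the same manner as specified in Section 7.7". On percent change, Section 7.7 says that "only MRI-PDFF relative change will include inferential statistics". Section 10 states: "There were no changes from the protocol planned analyses".

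**The concern.** The protocol's plan, the short list in SAP 7.18 and the declaration in Section 10 cannot all stand. A programmer who follows the SAP would produce no between-group estimate for trough 7αC4, bile acids or most of the lipid panel, and the study report could inherit a false statement that nothing changed.

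Two losses matter most. Trough 7αC4 is the measure from which the earlier TERN-101 study inferred sustained hepatic FXR engagement at 10 and 15 mg (protocol 2.2.2.2). It would be the natural all-patient check of that engagement for TERN-101 10 mg alone and in combination. Apo B differed significantly from placebo on Day 15 at 3 and 6 mg of TERN-501 in the first-in-human study (protocol Table 3), and both doses are used here. If these comparisons are left unspecified, markers, visits and scales could be chosen after unblinding.

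**Working it through.** The plan states no figure to reproduce. The check is a comparison of texts and a count.

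**1. Markers.** Protocol Table 9 lists 9 lipids: total cholesterol, triglycerides, LDL cholesterol, VLDL, non-HDL cholesterol, LDL particle number, apo B, apo A1 and lipoprotein(a). SAP 7.18 names one, so 9 − 1 = 8 have no model. Over all PD markers, SHBG + 9 lipids + FGF19 + 7αC4 + bile acids = 13. Two are assigned to the ANCOVA and 13 − 2 = 11 are not.

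**2. Does another SAP section supply the model?**
- The SAP assigns markers to Section 7.7 one at a time (liver enzymes in 7.9, fibrosis biomarkers in 7.10, rT3 in 7.11, the scores in 7.12 to 7.15, TE and CAP in 7.16). There is no catch-all.
- Section 8.3 gives descriptive summaries of the protocol Appendix 1 tests. Four of the eight lipids are in that list (total cholesterol, triglycerides, VLDL, non-HDL). Four are not (apo B, apo A1, lipoprotein(a), LDL particle number).
- Section 5 points to a safety analysis of lipids in Section 8.3.3, but 8.3.3 covers sex hormones.
- For bile acids, Section 7.18 gives only a rule for values below quantification: "FGF19, and bile acids that are BLQ will be set to" half the limit.
- Section 7.18.2 models derived parameters only: AUC for 7αC4 and FGF19, Cmin for 7αC4 and Cmax for FGF19. The model is an ANOVA with treatment alone. These parameters need intensive sampling, so they come from about 42 patients, about 6 per arm.

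**3. Trough samples outside any model.** Post-baseline trough 7αC4 is planned at Weeks 2, 4, 6 and 12 in 140 patients: 4 × 140 = 560 values. Section 7.18 says "Week 12 will include pre dose and all post dose assessments", so the Week 12 pre-dose values of about 42 sub-study patients do feed the 7.18.2 parameters. The rest is 560 − 42 = 518, and 518/560 = 92.5%. With 10% missing (an assumption), this is 0.9 × 518 ≈ 466 of 0.9 × 560 = 504. Bile acids: 140 Week 12 values (126 with 10% missing).

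**4. Precision.** The standard error of a group difference at 6 rather than 20 per arm is larger by √(20/6) = 1.83 if the SDs are equal. That is an assumption, because AUC or Cmin and a change in trough level are different quantities. The omitted trough ANCOVA, with 7 arms and one covariate, has 140 − 8 = 132 degrees of freedom. Its 95% half-width is 1.978 × √(2/20) = 0.63 residual SD. At 18 per arm it is 1.980 × √(2/18) = 0.66.

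**5. Percent change.** SAP 7.7 fits the ANCOVA to change and to relative change, and keeps LS means, standard errors and 95% intervals for relative change. Only further inferential statistics are confined to MRI-PDFF.

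**6. Comparisons.** SAP Table 6 has every active arm versus placebo, and each combination versus its TERN-501 dose. It has no combination versus TERN-101. The exploratory objective in protocol Section 3 covers target-engagement markers for the combination against placebo and/or each monotherapy.

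**7. Covariate in 7.18.2.** For a correlation ρ between the pre-dose value and the outcome, the standard error falls by 1 − √(1 − ρ²): 4.6% at 0.3, 13.4% at 0.5 and 40.0% at 0.8. The documents give no ρ. The lost degree of freedom costs a factor t(34)/t(35) = 1.001.

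**The case against.** The best defence is that this is a drafting slip in an exploratory part of the plan. The sentence in 7.18 has a stray comma after LDL-c and reads as a list cut short, so the signed SAP should be checked for lost items. Output shells that might fill the gap are not public. Protocol 9.4 leaves details to the SAP, 9.4.4.1 calls exploratory efficacy comparisons nominal and descriptive, and 9.4.4.3 still fixes markers, model and scales, so the analyses could be run without any new decision. This argues for low severity. It does not make the SAP complete or Section 10 true: removing a named model for named markers is a change, not a detail.

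Three stronger readings are tempting, and the documents do not support them.

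- *A reader might infer that percent change in the PD markers loses all inference.* LS means, standard errors and 95% intervals stay where Section 7.7 applies. Protocol 9.4.2, whose model is borrowed, lists estimates and intervals and mentions no p-value. Protocol 9.1 states hypotheses only for MRI-PDFF and cT1.
- *A reader might infer that the sponsor's target-engagement evidence is discarded.* For TERN-501 it is not. The dose rationale in protocol 4.3 rests on SHBG and LDL cholesterol, and both are kept. Nor was LDL-c informative only at 10 mg: Table 3 flags only that dose on Day 15, but protocol 2.2.1.2 reports significant reductions at most treatment timepoints at 6 mg as well.
- *A reader might infer that the omitted markers are not reported at all, or that 7αC4 is never compared with placebo.* SAP 3.1 requires by-patient listings and sets general summary rules, 7.18.2 compares 7αC4 AUC and Cmin between arms, and 7.18.3 plots concentrations.

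**Conclusion.** The mismatch is real and minor. Trough 7αC4, bile acids and 8 of 9 Table 9 lipids have no between-group model in the SAP, although the protocol plans one, and Section 10 is inaccurate as written. The main loss is the all-patient comparison of trough 7αC4 and of the other lipids, including apo B. The undeclared percent-change restriction in 7.7 is a lesser narrowing. Primary and secondary results are unaffected.

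The counts assume 140 patients and full attendance unless stated. They measure how much planned data goes unmodelled; they do not measure bias. The conclusion also assumes that the list in 7.18 is as short in the signed SAP as in the public one.

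**What to change.** 1. In SAP 7.18, extend the Section 7.7 ANCOVA sentence to trough 7αC4, bile acids and the remaining Table 9 lipids in all patients. Use the Table 6 comparisons, plus each combination versus TERN-101 10 mg for the FXR markers. Table 6 alone would still leave out what TERN-501 adds to or changes in the TERN-101 effect on those markers.
2. In Section 10, declare any marker, scale or comparison dropped on purpose. Two examples are the percent-change restriction in 7.7 and trough FGF19. Leaving out the latter is defensible, since levels generally returned to baseline by 24 hours in the earlier TERN-101 study (protocol 2.2.2.2) and Cmax and AUC are planned.
3. In 7.18.2, add the Day 1 pre-dose value of the marker as a covariate. It costs one degree of freedom, and the gain depends on a correlation that the documents do not give.

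The cost is one longer sentence, one or two lines in Section 10, one model term, and existing table templates run on more parameters. No new samples or visits are needed.

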7.18.1. PD Parameter Data Handling

7.18.1.1. Calculation of AUC

AUCs will be calculated using linear up / log down trapezoidal rule. For any partial AUC determination (i.e., AUC over a dosing interval), nominal time will generally be used for the end of the interval. The minimum requirement for the calculation of AUC will be the inclusion of at least three consecutive plasma concentrations above the LLOQ, with at least one of these concentrations following C_{max} for FGF19 and C_{min} for $7\alpha C4$.

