Trough PD Sampling ^c		X	х	Х	х		х		Х	Refer to Appendix 2 for additional detail.
NASH/ Fibrosis Biomarkers ^c		х			х		х		х	Includes CK-18 (M30 and M65), ELF (PIIINP, TIMP-1, HA), and PRO-C3.
Intensive PK Sampling (PK/PD sub-study only)		х					Xi			Intensive PK sampling will be performed pre-dose and 1, 2, 4, 6, and 24 hours post the first dose of study drug on Week 0/Day 1, and at pre-dose and 1, 2, 4, 6, 24, 48, and 72 hours post last dose of study drug at Week 12. Patients should be instructed to hold their dose of study drug until after pre- dose and after 24-hour PK samples are collected. Refer to Appendix 2 for additional detail.
Intensive PD Sampling (PK/PD sub-study Only)		х					Xj			7α C4 and FGF19 will be collected at matching timepoints to Intensive PK sampling (above) except at Week 12 when 7α C4 and FGF19 will not be collected at 48 and 72 hours post dose. Refer to Appendix 2 for additional detail.
Clinical Laborator	y Procedure	es/Assessn	nents							
Patient Fasting	х	х	х	х	х	х	х	х	х	Patients must be in fasted state for at least 8 hours prior to blood collection and treatment administration, where applicable.

	Screening]	Freatmen	t Period ^f			Follow -Up ^b ET ^a		Notes	
Visit	Screening	Week 0	Week 2	Week 4	Week 6	Week 8	Week 12	Week 16			
Study Day		Day 1	15	29	43	57	85	113			
Schedule Window (days)	-42 days		± 3	± 3	± 3	± 3	± 3	-7 /+2		Patients discontinuing the study at any time for any reason (Early Termination) should complete the ET visit as soon as feasible and return for a Follow-Up visit 4 weeks (-7 days /+2 days) after the last dose of study drug.	
Chemistry ^e	x	x	x	x	x	x	x	x	X	Specific analytes are listed in Appendix 1. ALT and AST stability may be evaluated prior to randomization per Section 5. Increased monitoring criteria for elevated ALT and/or AST above 2×Baseline or above 5×ULN, and elevated ALP above 3×ULN are outlined in Appendix 3. A standard lipid test will be collected as part of the clinical chemistry at Screening to confirm eligibility (Appendix 1). During study treatment, lipid parameters for PD assessments listed in Table 9 of Appendix 2 will be collected and results will be blinded. HDL will remain unblinded and will be collected as part of clinical chemistry at all visits. Refer to Appendix 5 for the eGFR formula, to be calculated by central lab.	
Hematology ^c	х	Х	х	Х	Х	Х	Х	Х	x	Specific analytes are listed in Appendix 1.	

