7.18.2. Statistical Methods for PD Parameters

Plasma PD parameters will be summarized by treatment group using descriptive statistics (number of non-missing observations, arithmetic mean, SD, median, minimum, maximum,

CONFIDENTIAL

geometric mean, and geometric CV%). For the calculation of summary statistics, all NR and not calculated (NC) values in a data series will be set to missing.

Analyses of AUC for both $7\alpha C4$ and FGF19, C_{max} for FGF19, and C_{min} for $7\alpha C4$ at Day 1 and Week 12 will be carried out using an analysis of variance (ANOVA) model with the PD parameter as the dependent variable including treatment group as a fixed effect. The estimate of the LS means, SE, and 95% CIs will be presented by treatment group. Estimates of the LS mean difference for each pairwise comparison will be presented with associated the standard error of the difference, and 95% CI of the difference.

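### The minimum-data rule for the 7αC4 AUEC discards computable profiles; if TERN-101 pushes values below the LLOQ, those lost tend to be the most suppressed

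*SAP*

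**What the plan says.** SAP 7.18.1.1 sets the minimum data for a PD AUC as the "inclusion of at least three consecutive plasma concentrations above the LLOQ, with at least one of these concentrations following" the extreme value, which is Cmin in the case of 7αC4 and Cmax in that of FGF19. The parameter concerned, in SAP Table 10, is the "Area under the effect-time curve from time 0 to 24 hours postdose"; RAUEC is its Week 12/Day 1 ratio.

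Three other rules bear on it:

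- SAP 7.18: concentrations of 7αC4, "FGF19, and bile acids that are BLQ will be set to" half the BLQ value.
- SAP Table 10, for Cmin: "In the case where multiple minimums are of equal magnitude, the earliest minimum concentration will be reported as" Cmin.
- SAP 7.18.2: for summary statistics, "all NR and not calculated (NC) values in a data series will be set to missing". The ANOVA described next names no method for a missing AUEC, so it runs on the profiles that remain.

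On sampling, the Protocol's Schedule of Activities states: "Intensive PK sampling will be performed pre-dose and 1, 2, 4, 6, and 24 hours post the first dose of study drug". 7αC4 and FGF19 "will be collected at matching timepoints to Intensive PK sampling (above) except at Week 12", where the 48 h and 72 h samples are for PK only. Each 7αC4 profile therefore has six samples: 0, 1, 2, 4, 6 and 24 h.

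**The concern.** The requirement resembles the drug-concentration rule in SAP 7.17.2 but is stricter. That rule asks for a point after Cmax only when there are just three consecutive values, and allows an exception for a metabolite. The PD rule always asks for a later point and has no exception.

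For a drug concentration, a value below the LLOQ carries little information. For 7αC4 the drug effect is a fall: Protocol 2.2.2.2 reports significant trough declines with TERN-101 10 mg, and Protocol 4.3 takes that dose to be at or near maximal target engagement. A BLQ value is then a strong response, and a rule that discards profiles for holding too many of them makes missingness depend on the outcome.

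The after-Cmin clause is a separate matter. No 7αC4 sample is scheduled after 24 h, so a profile that is lowest at 24 h can never qualify. Yet AUEC0-24 ends at 24 h and needs no extrapolation.

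**Working it through.** The plan states no LLOQ, BLQ rate, AUEC effect or AUEC power, so there is no figure to reproduce. Two checks were made.

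**1. The rule on its own (no assumptions about patients).** Six samples, each BLQ or not, give 2^6 − 1 = 63 patterns with at least one BLQ value. BLQ values are set to half BLQ, so the earliest BLQ value is Cmin. On the literal (strict) reading, the run of three quantifiable values must contain a point after Cmin. A BLQ Cmin breaks any run, so the whole run must lie after the first BLQ value:

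- first BLQ at 0 h: 8 of 32 patterns keep the AUEC
- first BLQ at 1 h: 3 of 16
- first BLQ at 2 h: 1 of 8
- first BLQ at 4, 6 or 24 h: 0 of 4 + 2 + 1 = 7

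Kept: 8 + 3 + 1 = 12. Lost: 63 − 12 = 51. By number of BLQ values:

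| BLQ values | Lost, strict | Lost, lenient |
|---|---|---|
| 1 | 3 of 6 | 1 of 6 |
| 2 | 9 of 15 | 7 of 15 |
| 3 | 17 of 20 | 17 of 20 |
| 4 to 6 | 22 of 22 | 22 of 22 |

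The strict column sums to 3 + 9 + 17 + 22 = 51. The lenient reading accepts any run of three plus any quantifiable value after Cmin. These are counts of patterns, not probabilities. A profile that is BLQ throughout is always lost, although half BLQ gives it a defined area of 24 × LLOQ/2 = 12 × LLOQ.

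**2. Direction and possible size (simulation).** Assumed, not from the documents: 20,000 patients per arm; lognormal baseline (log SD 0.6); log SD 0.8 for depth of suppression and 0.2 within patient; typical maximum suppression 60% or 85%; half or no recovery at 24 h on the log scale; LLOQ at 5% to 30% of typical baseline. AUEC0-24 is by linear-up/log-down. Entries are active/placebo geometric mean ratios; ranges run over the LLOQ.

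| Suppression, recovery | True | Strict rule | Lenient rule | Half BLQ, no count rule | Active lost (strict) |
|---|---|---|---|---|---|
| 60%, half | 0.44 | 0.51–0.77 | 0.46–0.64 | 0.44–0.46 | 12–50% |
| 85%, half | 0.22 | 0.40–0.74 | 0.32–0.56 | 0.24–0.31 | 33–76% |
| 60%, none | 0.35 | 0.44–0.71 | 0.42–0.62 | 0.35–0.39 | 38–65% |
| 85%, none | 0.15 | 0.31–0.64 | 0.28–0.52 | 0.17–0.25 | 54–84% |

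Placebo loses 16% to 20% under the strict rule. The ratio moves toward 1 in every case. So does the untransformed mean difference, which the ANOVA as written would use: with 60% suppression and half recovery it is about −14.5 with all profiles kept and −13.7 to −8.1 under the strict rule (typical baseline × hours).

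**The after-Cmin clause alone.** With an LLOQ near zero, essentially only this clause acts. It removes 2% to 34% of active and about 17% of placebo profiles; the placebo figure is what six exchangeable samples give, 1/6 = 17%. The strict ratios become 0.436 → 0.430, 0.222 → 0.234, 0.346 → 0.358 and 0.153 → 0.166: small shifts, not all in one direction.

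**The case against.** The strongest reply is that the bias is conditional. It needs BLQ values, and the documents give no LLOQ or BLQ rate; the earlier TERN-101 results in the Protocol describe declines and a plateau but mention no unquantifiable values. This stands, and it leaves the size open.

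A reader might also infer more than the documents support:

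- *That a lowest value at 24 h marks the strongest responders.* The clause selects on when the nadir occurs, not how deep it is. A deep nadir at 4 h with quantifiable values around it is kept; a flat profile with a chance minimum at 24 h is dropped.
- *That placebo is hardly touched.* About one placebo profile in six is lost to that clause in the simulation.
- *That all active arms are affected.* Protocol 9.4.4.3 lists 7αC4 as an FXR marker, and only three of the seven groups receive TERN-101. The mechanism is not shown for TERN-501 alone.
- *That the SAP contradicts itself.* The substitution and the threshold can operate together: half-BLQ values still feed Cmin, RCmin and any AUEC that meets the threshold. There is tension when many values are BLQ, not a contradiction.

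It is also fair that a depleted arm would be visible. SAP 7.18.2 reports the number of observations, SAP 7.18.3 plots the concentrations, and SAP 3.1 lists individual data. Visibility does not restore the lost profiles, however, and no sensitivity analysis covers them.

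**Conclusion.** The point holds in conditional form, as a minor one. If TERN-101 produces BLQ values, the rule tends to remove AUEC and RAUEC from the most suppressed patients in the three TERN-101 arms and to shrink the contrast with placebo. That the effect *is* biased toward none cannot be concluded: the actual loss is unknown, and the simulated sizes rest wholly on the assumed LLOQ, variability and suppression.

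The after-Cmin clause needs no BLQ values to act. It discards valid profiles in all arms for no computational reason, at a cost in precision and with no fixed direction of bias.

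Reach is limited. This is an exploratory sub-study parameter, and Cmin and trough 7αC4 are not subject to the rule. With about 6 patients per group, though, one lost profile is 1/6 = 17% of an arm and two are 2/6 = 33%.

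**What to change.** Amend SAP 7.18.1.1 for 7αC4 only:

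- count BLQ values, at the half-BLQ value that SAP 7.18 already assigns, as available samples;
- apply the three-sample minimum to non-missing samples;
- delete the condition that a value must follow Cmin;
- leave the FGF19 rule as it is, since no case against it is made here;
- report by arm the number of AUECs not calculated and the number resting mainly on imputed BLQ values.

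The cost is about one SAP sentence and two counts in a table. The downside is that a mostly BLQ profile yields a largely imputed AUEC, which should be flagged. Some shrinkage also remains where suppression is deep: in the 85%, half-recovery case, half BLQ gave 0.24 to 0.31 against a true 0.22, compared with 0.40 to 0.74 under the strict rule.
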